#### AND/OR

2. **Changes in the proliferation gene expression signature** post WOP intervention within the post-treatment biopsy compared to pre-treatment baseline biopsy.

#### Cohort D:

1. Change in CD8+ stromal tumour infiltrating lymphocyte (sTIL) frequency post anti-PD-L1 immunotherapy within the post-treatment biopsy compared to pre-treatment baseline biopsy.

#### AND/OR

2. **Changes in the Interferon Gamma-positive (IFNy**+) **signature** post WOP intervention within the post-treatment biopsy compared to pre-treatment baseline biopsy.

**Cohort A** (standard care reference cohort) will allow assessment of any biopsy effect on all co-primary endpoints assessed in treatment cohorts B, C and D.

#### **Cohorts F-G:**

1. **Change in mean proliferation index** (as measured by tumour cell Ki67 staining) post WOP intervention within the post-treatment biopsy compared to pre-treatment baseline biopsy.

#### AND/OR

2. **Changes in the proliferation gene expression signature** post WOP intervention within the post-treatment biopsy compared to pre-treatment baseline biopsy.

#### AND/OR

3. Changes in the plasma ctDNA (D0-D14) post WOP intervention compared to pre-treatment.

#### 4.2. Secondary Endpoints

- 1. Cohort E: Change in proliferation index and/or changes in proliferation gene expression signature and/or change in plasma ctDNA defined as per the primary endpoint for cohorts F-G.
- 2. Incidence of adverse events (AEs) during trial treatment (including surgical complications) by treatment cohort at 1 month post-surgery.
- 3. Methylation status of BRCA1 and RAD51C on diagnostic and pre- and post-WOP tumour samples and changes in methylation levels between these timepoints.

### 4.3. Exploratory Endpoints

- 1. Assess the ratio change in apoptosis and tumour cell proliferation in the post-treatment biopsy compared with pre-treatment baseline biopsy.
- 2. Relationship between the primary and secondary endpoints with the mutational landscape of the treated tumour as assessed by deep sequencing of the primary and residual disease and any subsequent metastatic relapse tumour genome and of tumour ctDNA in plasma.
- 3. Descriptive relationship between changes in ctDNA in Part 2 (post surgery) compared to biomarkers response to PART 1 in all patients from cohorts B-G.
- 4. Descriptive relationship between response status in PART 1 and changes in ctDNA in PART 2 within patients from cohorts B-G identified as ctDNA positive 30 days/3 months post-surgery who receive trial treatment in PART 2.
- 5. Descriptive relationship between ctDNA mutational profile in mutated genes in ctDNA pre-treatment and post-treatment ctDNA profiles in patients in both PART 1 and PART 2.
- 6. Descriptive differences in time between ctDNA detection and time to recurrence by 2 years in both the treated groups and observation group in PART 2.
- 7. RAD51 foci and geminin scoring on pre-wop biopsy samples
- 8. Methylation status of other HRD genes (including but not limited to BRCA2 and XRCC3) on diagnostic and pre- and post-WOP tumour samples, and the changes in methylation status between these timepoints.
- 9. Changes in phosphorylation of ataxia telangiectasia and Rad3-related protein (ATR) and its downstream effectors (including but not limited to Chk1, γH2AX, pKAP1, TAO upon drug exposure: including but not limited to levels of phosphorylation of p53, p38, p21/p27, cyclin dependent kinases (CDC25)).
- 10. Changes in biomarkers of DDR and adaptive and innate response, including but not limited to 53BP1, RAD51, RAD51C, RPA, RPA32, pRPA, BRCA1/2, PARP proteins, Shieldin complex components expression and immune checkpoint ligands and receptors and adaptive and innate immune response markers (IFNγ, cGAS-STING pathway, NKG2D receptors, ligands and cell markers) in the post-treatment biopsy compared to pre-treatment baseline biopsy using gene expression profiling.
- 11. Changes in biomarkers of DDR and adaptive and innate response, including but not limited to 53BP1, RAD51, RAD51C, RPA, RPA32, pRPA, BRCA1/2, PARP proteins, Shieldin complex components expression and immune checkpoint ligands and receptors and adaptive and innate immune response markers (IFNγ, cGAS-STING pathway, NKG2D receptors, ligands and cell markers) in the post treatment biopsy compared to pre-treatment baseline biopsy using reverse phase protein array (RPPA) and other proteome profiling.
- 12. Assessment of associated expression of co-inhibitory immune checkpoint receptors and ligands and frequency and function of TILs and myeloid cells subsets using immune cell markers and high content image de-convolution.
- 13. Changes in the levels of Th1/IFNy response as measured by transcriptional and proteomic profiling.
- 14. Immune cell population sub-set characterisation using appropriate and T and B cell receptor DNA sequencing methodologies.
- 15. Assess change in the Ki67:CD8+ ratio within the post-treatment biopsy compared to pre-treatment baseline biopsy.
- 16. HRD status according to Myriad MyChoice and Genomics England testing.

IRAS Project Number: 249774

### 5. SELECTION OF PARTICIPANTS FOR TRIAL REGISTRATION

### 5.1. Number of Participants

A maximum of 81 evaluable patients will be recruited into cohorts A-D of the trial and 38 recruited into cohorts E-G.

### **PART 1:**

Cohort A – 9 patients (closed)

Cohort B - max. 24 patients (closed)

Cohort C - max. 24 patients (closed)

Cohort D - max. 24 patients (closed)

Cohort E – max. 15 patients

Cohort F – max. 8 patients

Cohort G - max. 15 patients

#### **PART 2:**

### Cohorts A-D (cohorts closed from protocol Version 9.0)

Any patients with a ctDNA positive result at ctDNA screening at 30 days post-surgery or 3 months post-surgery will be given the opportunity to receive trial treatment in PART 2 provided they are confirmed suitable to commence treatment. Therefore a maximum of 81 patients may receive trial treatment within PART 2 cohorts A-D, however it is anticipated that the number of patients identified as ctDNA positive at this time point will be substantially lower (approx. 20%).

### **Cohorts E-G**

All patients in cohorts F and G will be given the opportunity to receive trial treatment in PART 2 provided they are confirmed suitable to commence trial treatment. Patients in cohort E will not be eligible for trial treatment in PART 2. Therefore, a maximum of 23 patients may receive trial treatment within PART 2.

### 5.2. Source of Participants

Participants will be recruited from approximately 20 participating sites in the UK. This will include a network of screening only and treatment delivery sites as described in Section 20. Potential participants will be identified in oncology clinics and discussed at Multi-Disciplinary Team (MDT) meetings.

Patients identified as poor responders to NACT and likely to have ≥1cm residual disease after NACT following mid-assessment imaging as per standard imaging guidelines will be approached to consent for Trial Registration. Registered patients with confirmed residual disease ≥1 cm on trial-specific imaging performed at least 1 week following day 1 of the final cycle of NACT will be invited to consent for Trial Entry.

### 5.3. Eligibility Criteria for Trial Registration

Patients will be considered eligible for Trial Registration if they fulfil all eligibility criteria listed below. Additional eligibility criteria for Trial Entry apply and must be confirmed prior entering a patient into the trial, please refer to Section 8.1.

IRAS Project Number: 249774

Patients who have participated in previous clinical trials (for this episode of breast cancer) may still enter PHOENIX, provided they meet all the eligibility criteria and participation in multiple trials will not compromise endpoint evaluation in either.

## 5.3.1. Inclusion Criteria for Trial Registration

- 1. Signed Informed Consent Form (ICF) for Trial Registration;
- 2. Aged ≥18 years old;
- 3. Histologically confirmed invasive triple negative breast cancer (TNBC). TNBC defined as ER negative, PgR negative (ER and PgR negative as defined by Allred score 0/8, 1/8 or 2/8 or stain in <1% of cancer cells) or PgR unavailable, and HER2 negative (immunohistochemistry 0/1+ or negative in situ hybridization) as determined by local laboratory and recorded in the patients notes;
- 4. Planned definitive surgical treatment after at least 6 cycles of neoadjuvant chemotherapy (NACT) Patients currently receiving SOC pembrolizumab, or having previously received SOC pembrolizumab but subsequently discontinued treatment, in combination with NACT are eligible for Trial Registration;
- 5. Radiographically measurable tumour mass assessable for new distinct radio-opaque marker insertion and repeated biopsies on the NACT mid-assessment standard of care imaging modality;
- 6. Eastern Oncology Cooperative Group (ECOG) performance status 0-1;
- 7. Considered fit enough to have breast cancer surgery with curative intent;
- 8. Considered fit to complete at least 2 weeks of pre-operative trial treatment in the WOP;
- 9. Patients must be suitable for a mandatory pre-treatment baseline biopsy performed Day -1 or 1 of the window of opportunity (WOP) and a post-treatment biopsy performed on Day 14 of the WOP. Registered patients who are approached for Trial Entry will be required to consent to the pre- and post- WOP treatment biopsy. If it is deemed unsafe to proceed with biopsy upon Trial Entry the patient will not be eligible for participation in the trial.
- 10. Patients with clinical stage II or III disease or clinical suspicion of metastatic disease must have staging studies to exclude metastatic disease if this is standard of care, and staging methods should be used as per standard of care (axillary lymph nodes or internal mammary node involvement will not be regarded as evidence of metastatic disease);
- 11. Patients with previous invasive cancers (including breast cancer) are eligible if the treatment was completed >5 years prior to Trial Registration, and there is no evidence of recurrent disease;
- 12. Absence of any psychological, familial, sociological or geographical condition potentially hampering compliance with the trial protocol and follow-up schedule; those conditions should be discussed with the patient before Trial Registration;
- 13. Patients must be a) surgically sterile (*i.e.* if female have undergone a hysterectomy, bilateral salpingectomy or bilateral oophorectomy; if male have undergone a bilateral orchidectomy); b) have a sterilised sole partner; or c) be post-menopausal; or d) must agree to practice total/true abstinence; or e) use a condom and one highly effective form of contraception in combination during the period

of trial treatment and be willing to do so for a period of at least 6 months following the end of trial treatment. Please refer to Section 5.4 Lifestyle Guidance for the definition of total/true abstinence and a list of the permitted highly effective forms of contraception.

Post-menopausal is defined by at least one of the following criteria:

- a. Amenorrhoeic for 1 year or more following cessation of exogenous hormonal treatments
- b. Luteinizing hormone (LH) and follicle stimulating hormone (FSH) levels in the postmenopausal range for the institution for women < 50 years of age not using hormonal contraception or hormonal replacement therapy. *Please note: in absence of amenorrhea for* 1 year, a single LH and/or FSH measurement is insufficient.
- c. Radiation-induced oophorectomy with last menses >1 year ago
- d. Chemotherapy-induced menopause with >1 year interval since last menses
- e. Surgical sterilisation (hysterectomy, bilateral salpingectomy or bilateral oophorectomy)

### 5.3.2. Exclusion Criteria for Trial Registration

- 1. Definitive evidence of metastatic disease (axillary lymph nodes or internal mammary node involvement will not be regarded as evidence of metastatic disease);
- 2. Patients with bilateral tumours.
- 3. History of another primary malignancy within the last 5 years prior to Trial Registration, except for:
  - Adequately treated non-melanoma skin cancer or lentigo maligna without evidence of disease;
  - b. Adequately treated carcinoma in situ without evidence of disease;
- 4. Patients with myelodysplastic syndrome (MDS)/acute myeloid leukaemia (AML) or with features suggestive of MDS/AML;
- 5. Severe concurrent disease, infection or co-morbidity that, in the judgment of the local Investigator, would make the patient inappropriate for Trial Registration;
- Resting ECG indicating uncontrolled, potentially irreversible cardiac conditions, as judged by the investigator (e.g., unstable ischemia, uncontrolled symptomatic arrhythmia, congestive heart failure, QTcF prolongation >470 msec, electrolyte disturbances, etc.), or patients with congenital long QT syndrome;
- 7. Patients unable to swallow orally administered medication;
- 8. Patients receiving therapeutic anti-coagulation treatment (including warfarin and novel oral anti-coagulants).
- 9. Patients with gastrointestinal disorder affecting absorption (e.g. gastrectomy, active peptic ulcer disease within last 3 months);

40

IRAS Project Number: 249774

- 10. History of seizure or any condition that may predispose to seizure.
- 11. Other non-malignant systemic disease that would preclude trial treatment or would prevent required follow-up;
- 12. Pregnant or breast-feeding;
- 13. Prior exposure to PARP inhibitor, including olaparib, anti-PD-1 or anti-PDL1 immunotherapy (including durvalumab) except for pembrolizumab if received as standard of care in combination with neoadjuvant chemotherapy;
- 14. Any other disease(s), psychiatric condition, metabolic dysfunction, or findings from a physical examination or clinical laboratory test result that in the investigators opinion would cause reasonable suspicion of a disease or condition, that contraindicates the use of trial treatment, that may increase the risk associated with trial participation, that may affect the interpretation of the results, or that would make this trial inappropriate for the patient;
- 15. Patients with a known hypersensitivity to pembrolizumab, durvalumab or olaparib or any excipients of the products;
- 16. Previous allogenic bone marrow transplant or double umbilical cord blood transplantation (dUCBT);
- 17. Active infection including tuberculosis (TB) (clinical evaluation that includes clinical history, physical examination and radiographic findings, and TB testing in line with local practice), hepatitis B (HBV; known positive HBV surface antigen (HBsAg) result), hepatitis C (HCV), or human immunodeficiency virus (HIV; positive HIV 1/2 antibodies). Patients with a past or resolved HBV infection (defined as the presence of hepatitis B core antibody [anti-HBc] and absence of HBsAg) are eligible. Patients positive for HCV antibody are eligible only if polymerase chain reaction is negative for HCV RNA;

Please note, the following exclusion criteria will apply prior to Trial Entry. These criteria should be considered prior to Trial Registration with the expectation that the patient would not be excluded from Trial Entry based on these points:

- 1. History of clinically significant or uncontrolled cardiovascular disease including:
  - Myocardial infarction within 6 months prior to Trial Entry;
  - Uncontrolled angina within 3 months prior to Trial Entry;
  - Congestive heart failure New York Heart Association (NYHA) class III or IV, or patients with history of congestive heart failure NYHA class III or IV in the past, unless an echocardiogram (ECHO) or multi-gated acquisition (MUGA) scan performed within 3 months prior to Trial Entry results in a left ventricular ejection fraction that is 45%;
  - History of clinically significant ventricular arrhythmias (e.g. ventricular tachycardia, ventricular fibrillation, torsades de pointes);
  - History of Mobitz II second degree or third degree heart block without a permanent pacemaker in place;
  - Consistent evidence of hypotension as indicated by systolic blood pressure < 90 millimeters of mercury (mm Hg) prior to Trial Entry;
  - Consistent evidence of bradycardia as indicated by a heart rate of < 50 beats per minute on the ECG prior to Trial Entry;

IRAS Project Number: 249774

- Consistent evidence of uncontrolled hypertension as indicated by systolic blood pressure >
   170 mm Hg or diastolic blood pressure > 105 mm Hg prior to Trial Entry.
- 2. History of loss of consciousness or transient ischemic attack within 12 months prior to Trial Entry;
- 3. Patients with Grade ≥2 neuropathy, as defined by the National Cancer Institute (NCI)'s Common Terminology Criteria for Adverse Events Version 5.0 (NCI CTCAE v5.0) will be evaluated on a case-by-case basis after consultation with the CI or Coordinating Investigator;
- 4. Major surgery (excluding minor procedures, e.g. placement of vascular access) within 2 weeks prior to Trial Entry. *Patients must have recovered from any effects of any major surgery prior to commencing trial treatment.*
- 5. Use of any investigational agent within 30 days prior to commencing trial treatment.
- 6. Concomitant use of known strong CYP3A inhibitors (e.g. itraconazole, telithromycin, clarithromycin, protease inhibitors boosted with ritonavir or cobicistat, indinavir, saquinavir, nelfinavir, boceprevir, telaprevir) or moderate CYP3A inhibitors (e.g. ciprofloxacin, erythromycin, diltiazem, fluconazole, verapamil) within 2 weeks prior to first dose of trial treatment. The required washout period prior to commencing trial treatment is 2 weeks;
- 7. Concomitant use of known strong (e.g. phenobarbital, enzalutamide, phenytoin, rifampicin, rifabutin, rifapentine, carbamazepine, nevirapine and St John's Wort) or moderate (e.g. bosentan, efavirenz, modafinil) CYP3A inducers. *The required washout period prior to commencing trial treatment is 5* weeks;
- 8. Whole blood infusion or erythropoietin within 28 days prior to trial entry (packed red blood cells and platelet transfusions are acceptable).
- 9. Receipt of live attenuated vaccine within 30 days prior to commencing trial treatment.

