8.1.1. Inclusion Criteria for Trial Entry

1. Signed Informed Consent Form (ICF) for Trial Entry;

2. Residual disease is confirmed as at least one viable disease focus ≥1cm on trial-specific imaging

performed at least 1 week following day 1 of the final cycle of NACT.

3. Provision of acceptable archival diagnostic tumour tissue sample prior to Trial Entry as defined in the

Investigator Laboratory Manual.

4. Recovery from all acute adverse events of prior NACT or pembrolizumab to baseline or NCI CTCAE Grade ≤1, except for alopecia. Patients with irreversible toxicity not reasonably expected to be exacerbated by trial treatment may be included only after consultation with the CI or Coordinating

Investigator.

5. Patients must have adequate haematological, renal and hepatic function as defined by:

- Haemoglobin (Hb)  $\geq$  10 g/dL ( $\geq$  100 g/L) with no blood transfusion in the past 28 days

- Absolute neutrophil count (ANC)  $\geq$  1500/mm^3 ( $\geq$  1.5 x 10^9/L)

- Platelet count ≥100,000/mm^3 (≥ 100 x  $10^9$ /L)

PHOENIX Protocol Version: 10.0, 23 April 2025

45

IRAS Project Number: 249774

- Total bilirubin  $\leq 1.5 \text{ x}$  institutional upper limit of normal (ULN)
- Aspartate aminotransferase (AST) (Serum Glutamic Oxaloacetic Transaminase (SGOT)) /
  Alanine aminotransferase (ALT) (Serum Glutamic Pyruvate Transaminase (SGPT)) ≤ 2.5 x
  institutional ULN
- Calculated creatinine clearance ≥51 mL/min using the Cockcroft-Gault equation (please refer to Appendix 4) or based on a 24 hour urine test or another validated test as per local practice
- 6. Women of childbearing potential must have a confirmed menstrual period and a negative urinary or serum pregnancy test prior to Trial Entry. This should be repeated as applicable to ensure a negative pregnancy test is performed on the day of planned trial treatment.
- 7. Confirmation that all Trial Registration inclusion criteria listed in Section 5.3.1 remain satisfied.

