### 8.1.2. Exclusion Criteria for Trial Entry

- 1. Patients considered a poor medical risk due to a serious, uncontrolled medical disorder, non-malignant systemic disease or active, uncontrolled infection. Examples include, but are not limited to, uncontrolled ventricular arrhythmia, recent (within 3 months) myocardial infarction, uncontrolled major seizure disorder, unstable spinal cord compression, superior vena cava syndrome, extensive interstitial bilateral lung disease on High Resolution Computed Tomography (HRCT) scan or any psychiatric disorder that prohibits obtaining informed consent.
- 2. Major surgery (excluding minor procedures, e.g. placement of vascular access) within 2 weeks prior to Trial Entry. *Patients must have recovered from any effects of any major surgery prior to commencing trial treatment.*
- 3. Use of any investigational agent within 30 days prior to commencing trial treatment.
- 4. Concomitant use of known strong CYP3A inhibitors (e.g. itraconazole, telithromycin, clarithromycin, protease inhibitors boosted with ritonavir or cobicistat, indinavir, saquinavir, nelfinavir, boceprevir, telaprevir) or moderate CYP3A inhibitors (e.g. ciprofloxacin, erythromycin, diltiazem, fluconazole, verapamil). The required washout period prior to commencing trial treatment is 5 weeks;
- 5. Concomitant use of known strong (e.g. phenobarbital, enzalutamide, phenytoin, rifampicin, rifabutin, rifapentine, carbamazepine, nevirapine and St John's Wort) or moderate (e.g. bosentan, efavirenz, modafinil) CYP3A inducers. The required washout period prior to commencing trial treatment is 5 weeks;
- 6. Whole blood infusion within 28 days prior to trial entry (packed red blood cells and platelet transfusions are acceptable).
- 7. Receipt of live attenuated vaccine within 30 days prior to commencing trial treatment.
- 8. Confirmation that none of the Trial Registration exclusion criteria listed in Section 5.3.2 are met.

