### 24.4. Part 1 Olaparib: Permitted Concomitant Therapy

Patients who are receiving neoadjuvant pembrolizumab as SOC can continue this treatment during Part 1 of the trial. All other medication considered necessary for the participants' welfare and which is not expected to interfere with the evaluation of the trial treatment may be given at the discretion of the investigator. All concomitant medications must be recorded in the patient's notes, as well as the appropriate eCRF pages within the clinical database.

The use of any natural/herbal products or other traditional remedies should be discouraged, but use of these products, as well as use of all vitamins, nutritional supplements, and all other concomitant medications must be recorded in the eCRF.

Bisphosphonates, RANK ligand antagonists (e.g. denosumab) and blood transfusions should be given as required at the discretion of the Investigator.

Patients may take corticosteroids but increased vigilance is recommended on electrolyte and glucose levels.

Patients who require anti-coagulation during trial treatment should start on LMWH.

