#### **Anticoagulant Therapy**

Patients who are taking warfarin may participate in this trial; however, it is recommended that international normalised ratio (INR) be monitored carefully at least once per week for the first month, then monthly if the INR is stable. Subcutaneous heparin and low molecular weight heparin are permitted.

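### The eligibility text contradicts itself on warfarin, on CYP3A-inhibitor washout and on recent red-cell transfusion; the stricter rule wins on a strict reading, but the looser text invites ineligible entries

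*Protocol*

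**What the plan says.** **Warfarin.** Exclusion 8 of Section 5.3.2 (Trial Registration) rules out "Patients receiving therapeutic anti-coagulation treatment (including warfarin and novel oral anti-coagulants". Exclusion 8 of Section 8.1.2 (Trial Entry) carries the registration exclusions forward: "Confirmation that none of the Trial Registration exclusion criteria listed in Section 5.3.2 are met". Under Anticoagulant Therapy in Section 24.5 (Part 1 olaparib), and again in Section 25.2.8 (Part 2 olaparib), the protocol says "Patients who are taking warfarin may participate in this trial", with INR monitoring. Section 24.4 adds "Patients who require anti-coagulation during trial treatment should start on LMWH".

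**CYP3A inhibitors.** Section 5.3.2 ends with a second list, introduced as criteria that will apply before Trial Entry. Its item 6, on strong or moderate inhibitors, says "The required washout period prior to commencing trial treatment is 2 weeks". For the same drugs, exclusion 4 of Section 8.1.2 says "The required washout period prior to commencing trial treatment is 5 weeks". Sections 24.5 and 25.2.8 also give 5 weeks and refer to Section 8.1.2.

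**Transfusion.** Inclusion 5 of Section 8.1.1 requires haemoglobin of at least 10 g/dL "with no blood transfusion in the past 28 days". Exclusion 6 of Section 8.1.2 bars only whole blood in the 28 days before entry and adds that "packed red blood cells and platelet transfusions are acceptable". Item 8 of the second list in Section 5.3.2 says the same but also names erythropoietin, which Section 8.1.2 leaves out.

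**The concern.** Each topic has one statement that excludes a patient and another that tells the site the patient is acceptable. Both are in the current version 10.0 text, so this is not a leftover from the amendment log. A site that reads the looser statement can enter an ineligible patient in good faith. A monitor who then has to classify the deviation will find protocol text on both sides.

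The topics are safety-relevant by the protocol's own schedule. Every patient has a core-biopsy session at the start of the window, another on Day 14, and then surgery, around olaparib and soon after chemotherapy. Inhibitor exposure also matters on the protocol's own account: Appendix 5 ties concurrent inhibitors to a lower olaparib dose, while Section 24.1.3 allows no dose modification in the window.

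**Working it through.** There is no sample-size or power figure to reproduce. The check sets the statements side by side and identifies the patients for whom they give different answers.

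| Topic | Stricter statement | Looser statement | Patients on whom they disagree |
|---|---|---|---|
| Warfarin | 5.3.2 exclusion 8, re-applied by 8.1.2 exclusion 8 | 24.5; less directly 25.2.8 | Anyone taking warfarin therapeutically |
| CYP3A-inhibitor washout | 8.1.2 exclusion 4, 24.5, 25.2.8: 5 weeks | 5.3.2 second list, item 6: 2 weeks | Last inhibitor at least 2 but less than 5 weeks (14 to 34 days) before first olaparib |
| Transfusion | 8.1.1 inclusion 5 | 8.1.2 exclusion 6; 5.3.2 second list, item 8 | Haemoglobin at least 10 g/dL with packed red cells in the last 28 days |

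**Warfarin.** The Section 24.5 sentence is worded as a rule on participation. It is not advice for anticoagulation that starts during treatment, which Section 24.4 covers separately. Its INR schedule (weekly for the first month, then monthly) also does not fit the 14-day treatment it sits under. The Part 2 copy is a weaker contradiction: it applies after surgery, and Section 12.1 lists no anticoagulant exclusion for Part 2.

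**Washout.** The window starts at least 3 weeks (21 days) after day 1 of the final chemotherapy cycle. Let *t* be the day of the last inhibitor dose, counted from that day 1. At the earliest start the gap is 21 − *t* days.
- 2-week rule: 21 − *t* ≥ 14, so *t* ≤ 7.
- 5-week rule: 21 − *t* ≥ 35, so *t* ≤ −14.

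At the earliest start the rules therefore disagree for a last dose from 13 days before to 7 days after day 1. This is not forced on every patient. The protocol gives a minimum start but no maximum, and a patient with *t* = 7 meets the 5-week rule once the window opens at 7 + 35 = 42 days.

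**Transfusion.** For entry no later than 21 days after day 1 of the final cycle, a 28-day look-back reaches at least 28 − 21 = 7 days before that day 1. A red-cell transfusion at any time in the final cycle before such an entry then falls inside it. The conflict is clear for packed red cells. It is arguable for platelets, because the 28-day clause in Section 8.1.1 is attached to the haemoglobin value.

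**How the criteria combine.** Section 8.1 requires all Trial Entry criteria to be met, and exclusion 8 of Section 8.1.2 brings in the registration exclusions. Read strictly, the warfarin patient, the patient 14 to 34 days off an inhibitor and the patient recently given red cells are each excluded.

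**The case against.** The strongest reply is that the criteria are cumulative, so there is already one answer in each case. A reader might infer that sites may validly enter or exclude the same patient. The documents do not support that, for the reason just given: the stricter rule governs. What remains is looser text that has no effect if the reader applies everything and misleads if the reader does not.

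Other parts of the reply also stand.
- The warfarin permission sits in concomitant-medication sections, not in the eligibility lists.
- The LMWH sentence in Section 24.4 concerns patients who come to need anticoagulation during treatment, so it does not contradict the exclusion.
- The 2-week washout is one line in a list meant for forward planning at registration, against three places that say 5 weeks. It is still stated as a required washout in a list said to apply before Trial Entry.
- Entry is central, on a signed checklist (Section 9). The checklist is not in the protocol and may already apply a single rule, so variation between sites is possible but not shown.
- There are safeguards. Patients for whom biopsy is unsafe are ineligible, fitness for surgery is required (Section 5.3.1), and clotting and blood counts are checked at baseline and Day 14 (Sections 11.1 and 11.2).

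Two further inferences should be resisted. The conflicts do not alter the evaluable population as the protocol defines it, because Sections 17.1.1 and 24.1.2 define evaluability by doses taken and paired samples. Nor do they affect all of the up to 38 evaluable patients (15 + 8 + 15) in cohorts E to G; they matter only for those with the exposures concerned.

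**Conclusion.** The three contradictions are real and in the current text, and they need correcting. The firmest are warfarin in Section 5.3.2 against Section 24.5, the 2-week against the 5-week inhibitor washout, and red-cell transfusion in Section 8.1.1 against Sections 5.3.2 and 8.1.2. The Part 2 warfarin sentence and the platelet wording are weaker. The erythropoietin difference is a smaller mismatch between two lists that should agree.

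The consequence is a risk of entering ineligible patients and of inconsistent deviation handling, with some safety relevance around biopsies and surgery. It bears on who is entered. It changes no endpoint, decision rule or sample-size figure. Its size cannot be computed, because the protocol gives no frequency for warfarin use, recent transfusion or inhibitor use. The conclusion assumes only that sites consult the protocol text as well as the checklists, which were not available to check.

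**What to change.** In the next amendment, reconcile the following to one rule each:
- **Anticoagulation:** exclusion 8 of Section 5.3.2 with the Anticoagulant Therapy text in Sections 24.5 and 25.2.8.
- **CYP3A-inhibitor washout:** item 6 of the second list in Section 5.3.2 with exclusion 4 of Section 8.1.2 and with Sections 24.5 and 25.2.8.
- **Transfusion:** inclusion 5 of Section 8.1.1 with exclusion 6 of Section 8.1.2 and item 8 of the second list in Section 5.3.2. State separately how red cells and platelets are treated, and make the two lists agree on erythropoietin.

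Then check that the Trial Registration and Trial Entry eligibility checklists carry the same rules. Which rule stands is for the medical team; none is proposed here. The cost is wording in an amendment and a check of two checklists, with no change to the design or analysis.
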